- NIAID ordinal scale: The ordinal scale is an assessment of the clinical status as follows: 1) Death; 2) Hospitalized, on invasive mechanical ventilation or extracorporeal membrane oxygenation (ECMO); 3) Hospitalized, on non-invasive ventilation or high flow oxygen devices; 4) Hospitalized, requiring supplemental oxygen; 5) Hospitalized, not requiring supplemental oxygen - requiring ongoing medical care (COVID-19 related or otherwise); 6) Hospitalized, not requiring supplemental oxygen - no longer requires ongoing medical care; 7) Not hospitalized, limitation on activities and/or requiring home oxygen; 8) Not hospitalized, no limitations on activities. (combined items 7 and 8 as our study is limited to hospital)

- 48 hour in-hospital mortality
- 14 days in-hospital mortality
- 28 days in-hospital mortality
- ICU-free days (up to 28 days)
- In-hospital coagulation-related event-free (arterial and venous) days (up to 28 days)
- Ventilator-free days (up to 28 days)
- Successful extubation (no re-intubation for >3 days after initial extubation)
- Successful weaning from paralysis for > 3 days after initial termination
- Survival to discharge

Sample size and Power Analysis: (Pass, 14.0, NCSS, LLC, Kaysville, Utah, USA)

We anticipate that each of the five centers will enroll 8-12 patients. Sample size and power Analysis was conducted using Pass, vs 14.0 (NCSS, LLC, Kaysville, Utah, USA) and focused on the primary outcome as defined above. Sample size assumptions:

- power=80%, confidence=95%, and 4 sequential tests(3 interim+1 final), using the Pocock spending function to determine test boundaries,
- potential improvement assumptions based on a previous study ⁴⁰ with appropriate(e.g., Denver) altitude correction as well as mean baseline PaO₂/FiO₂=149 with an overestimated standard deviation of 100,
- design effect=1.12 due to the study's multicenter nature (intra-class correlation coefficient=0.03, average cluster=5);
- ~20% inflation to account for premature death

A sample size of 50 (25 in each intervention group and 25 in the control group) patients detects a >70% improvement in PaO₂/FiO₂ between intervention groups (both tPA50 and tPA 50 plus drip) and controls, and >91% improvement in PaO₂/FiO₂ between intervention tPA 50 plus drip) and controls. Recruitment will assume at least 30% increase to account for refusal or inability to consent.

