Consent: We anticipate consenting enough patients to result in 50 eligible patients, thus we plan on a max of 60, to be re-evaluated during each of the interim analyses. LAR, as defined by the state and institutions legislation/policies, will be able to consent

It should be noted that using the traditional (yet arbitrary) confidence level of 95% (alpha=0.05) is not adequate in the current circumstances. The rigid cutoff around what we believe to be a 95% level of certainty, as eloquently put it by Nuzzo in one of the most cited Nature articles ⁴⁸, is inappropriate. Thus, for all comparisons, we will present the effect size with appropriate confidence intervals depicting the uncertainty surrounding our estimation. The clinical experience of the investigators working together with the independent DSMB will produce the appropriate interpretation of the results, which can then inform current medical decisions and the next Phase III trial.

Criteria for stopping the clinical trial early for efficacy or harm:

Stopping the clinical trial early for efficacy or harm
Reaching adjusted p-value for the primary outcome and at least one of the secondary outcomes at all follow-up time points
DSMB deemed harm profile unacceptable

Criteria for stopping for futility: we will follow the guidelines established by Jitlal et al ⁴⁹:

Stopping the clinical trial early for futility
•Low conditional power (<15%), calculated using PASS 14 with bootstrapping simulations, based on the target minimum differences for all primary and secondary outcomes at all follow-up time points.
•Observed difference size in the primary or secondary outcomes favor the control group (<5%) at all follow-up time points.
•The DSMB and trial team agree that enough patients and events have been observed so far to produce a reliable effect
•There are less than 2 centers interested in continuing enrollment
•There is no evidence of an effect in any pre-specified subgroups.
•The DSMB deemed the adverse events profile acceptable (if there are no safety concerns, we may wish to continue to ensure that a modest effect is not missed).

Adaptive design:

The study interim analyses will be used to propose pre-planned modifications based on observed effects, recruitment, eligibility and other aspects of the study as determined below.

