### Section 3: Study Methods

**3.1. Trial design** Multicenter, pragmatic, randomized, open label, rapidly adaptive, controlled, clinical trial

The trial has a novel design with modified stepped-wedge and adaptive features in order to rapidly identify the intervention group with the highest chance of benefit. This unconventional design is appropriate for the current circumstances of the pandemic caused by a new, lethal and morbid virus infection (COVID-19) for which no known treatment exists. The below figure illustrates the design. In brief, the patients will be sequentially assigned to one of three following groups:

[figure not shown]
[figure not shown]
- Group tPA50 will receive 50 mg of tPA intravenous bolus administration over 2 hours, given as a 10 mg push followed by the remaining 40 mgs over a total time of 2 hrs (not to exceed 0.9mg/kg dose). Immediately following the tPA infusion, 5000 U of UFH will be delivered and the heparin drip will be continued to maintain the activated partial thromboplastin time at 60-80sec (2.0 to 2.5 times the upper limit of normal). This tPA protocol is a modification of the GUSTO I to III trials. 44,45
- Group tPA50 plus drip will receive 50 mg of tPA intravenous bolus administration over 2 hours, given as a 10 mg push followed by the remaining 40 mgs over a total time of 2 hrs (not to exceed 0.9mg/kg dose). Immediately following this initial tPA infusion, we will initiate a drip of 2 mg/hr tPA over the ensuing 24 hours (total 48 mg infusion) accompanied by an infusion of 500 U/hr heparin during the tPA drip. After this, heparin dose will be increased slowly to maintain a PTT between 60 and 80 sec, titrated per attending's discretion.
- Control: institution's protocol for ARDS

In order to rapidly accrue patients in one intervention group with a concurrent control, the first 10 patients will be randomly assigned to Group tPA50 or Control (Standard-of-care) when the first interim analysis occurs. If no stopping criteria are met, the next 10 patients are randomly

assigned to Group tPA50 or Control when the second interim analysis is done. If no criteria for stopping or dropping an arm are met, the next 10 patients are randomly assigned to Group tPA50 plus drip or Control when the third interim analysis is done. Finally, if no criteria for stopping or dropping an arm are met, the trial progresses with patients being randomized to Group tPA50 plus drip or Control up to the final analysis at n=50.

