### 3.2. Sample size

We anticipate that each of the five centers will enroll 8-12 patients. Sample size and power Analysis was conducted using Pass, vs 14.0 (NCSS, LLC, Kaysville, Utah, USA) and focused on the primary outcome as defined above.

Sample size assumptions:

- power=80%, confidence=95%, and 4 sequential tests(3 interim+1 final), using the Pocock spending function to determine test boundaries,
- potential improvement assumptions based on a previous study 40 with appropriate(e.g., Denver) altitude correction as well as mean baseline PaO2/FiO2=149 with an overestimated standard deviation of 100,
- design effect=1.12 due to the study's multicenter nature (intra-class correlation coefficient=0.03, average cluster=5);
- ~20% inflation to account for premature death

---

 Urbaniak, G. C., & Plous, S. (2013). Research Randomizer (Version 4.0) [Computer software]. Retrieved on April 10, 2020, at <http://www.randomizer.org/>

A sample size of 50 (25 in each intervention group and 25 in the control group) patients detects a >70% improvement in PaO2/FiO2 between intervention groups (both tPA50 and tPA 50 plus drip) and controls, and >91% improvement in PaO2/FiO2 between intervention tPA 50 plus drip) and controls. Recruitment will assume at least 30% increase to account for refusal or inability to consent.

**Consent: We anticipate consenting enough patients to result in 50 eligible patients, thus we plan on a max of 60, to be re-evaluated during each of the interim analyses. LAR, as defined by the state and institutions legislation/policies, will be able to consent.**

The table below shows the details of the interim analyses with the Pocock spending method:

Look	N of Patients	Lower Bndry	Upper Bndry	Nominal Alpha	Inc Alpha	Total Alpha	Inc Power	Total Power
1	10	-2.43798	2.43798	0.015	0.015	0.015	0.18976	0.190
2	20	-2.42677	2.42677	0.015	0.011	0.026	0.25179	0.442
3	30	-2.41014	2.41014	0.016	0.009	0.035	0.21191	0.653
4	50	-2.39658	2.39658	0.017	0.008	0.043	0.14655	0.800

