It should be noted that using the traditional (yet arbitrary) confidence level of 95% (alpha=0.05) is not adequate in the current circumstances. The rigid cutoff around what we believe to be a 95% level of certainty, as eloquently put it by Nuzzo in one of the most cited Nature articles, is inappropriate. Thus, for all comparisons, we will present the effect size with appropriate confidence intervals depicting the uncertainty surrounding our estimation. The clinical experience of the investigators working together with the independent DSMB will produce the appropriate interpretation of the results, which can then inform current medical decisions and the next Phase III trial.

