### 6.4. Outcomes comparison:

All analyses will be conducted initially as an intent-to-treat (patients are analyzed in the group they were randomized to), followed by an as-treated analysis. The primary outcome will be assessed within group and between groups. Differences in the primary outcome will be assessed using linear mixed models, with appropriate transformations if normality departure of residuals is detected. Linear mixed models allows us to adjust for potential confounders detected in the comparison of the groups at baseline using inverse probability weighting by a propensity score, the covariance structure, the repeated measures and the intra-hospital correlation (as this is a multicenter study). In addition, it tolerates missing observations. We will also compare percent change over baseline, using t-tests with the appropriate adjustment for heteroscedasticity if needed. Categorical outcomes will be compared using generalized estimating equations to account for confounders (as above), covariance structure and intra-hospital correlation. In addition, we will compare the “dose” of the intervention (i.e., how much of the treatment the patient received) as the effect of interest, as premature death is, unfortunately, expected. Survival analysis with inverse probability weighted Cox proportional hazards model and robust sandwich variance estimate with clustering for hospitals will be used for mortality and for survivor-bias outcomes censoring for death (e.g., thrombotic complication). As all outcomes are in-hospital, loss to follow-up is not likely. The pre-planned comparisons include within group (improvement over baseline) and between groups, all two-tailed with significance declared as defined by the Pocock spending method.

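### The four-look Pocock correction reaches only the significance test; no sequentially adjusted estimate, interval method or interval level is specified for the effect size meant to guide Phase III

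*SAP*

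**What the plan says.** The Protocol (Sample size and Power Analysis) sets the design as "power=80%, confidence=95%, and 4 sequential tests(3 interim+1 final), using the Pocock spending function to determine test boundaries". SAP 3.2 prints the looks at 10, 20, 30 and 50 patients with boundaries 2.43798, 2.42677, 2.41014 and 2.39658. SAP 3.3 allows an efficacy stop when the adjusted p-value is reached for the primary outcome and at least one secondary outcome. SAP 6.4 names linear mixed models for the primary outcome, with comparisons "all two-tailed with significance declared as defined by the Pocock spending method".

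The same SAP section 3.2, and the matching paragraph of the Protocol, call the 95% level inadequate and turn to estimation instead: "Thus, for all comparisons, we will present the effect size with appropriate confidence intervals depicting the uncertainty surrounding our estimation". No replacement level is given. The results are then to inform current care and the next trial.

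Neither document says how the estimate or the interval should reflect the four looks.

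**The concern.** The sequential design is accounted for in the quantity the plan plays down and left open for the quantity it relies on. An estimate that stops a trial by crossing a boundary is selected for being large, so on average it overstates the effect. A mixed-model estimate with a 1.96-SE interval would comply with the SAP as written.

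The stakes are the effect size carried into Phase III planning, and an interval that may exclude zero where the governing test does not reject. A true effect below the design value is plausible. The 70% target rests on a previous study that the Protocol's reference list shows was done in pigs, while the trial's own adaptation thresholds are improvements of 20% and 50%.

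**Working it through.** **Inputs (SAP 3.2).** Two-sided alpha 0.05; the boundaries above; printed incremental power 0.18976, 0.25179, 0.21191, 0.14655; total alpha 0.043; total power 0.800; baseline 149; SD 100; 25 per arm; design effect 1.12; about 20% inflation for death.

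**Step 1: reproduce the table.** Pocock-type spending is α(t) = 0.05·ln(1 + (e − 1)t).
- At t = 0.2, 0.4, 0.6, 0.8 this gives 0.0148, 0.0262, 0.0354, 0.0432, which match the printed totals 0.015, 0.026, 0.035, 0.043.
- Recursive integration gives boundaries 2.43798, 2.42681, 2.41019, 2.39664.
- A drift of 3.118 at the last look gives incremental power 0.1897, 0.2518, 0.2119, 0.1466, total 0.800.
- SE at the last look = 100·√(2/(25 × 0.8/1.12)) = 33.47. Then 3.118 × 33.47 = 104.3 points, and 104.3/149 = 70.0%.

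The table therefore reproduces, but row 4 is labelled N=50 while it carries the boundary and cumulative alpha for t = 0.8. At t = 1 the last boundary would be 2.281 and total alpha 0.050. Relative to the last look, the timing behind the power column is 0.25, 0.5, 0.75, 1.

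**Step 2: bias at look 1, exactly.** Expected z = 3.118 × √0.25 = 1.559. Distance to the boundary a = 2.43798 − 1.559 = 0.879. Crossing probability 1 − Φ(0.879) = 0.1897. Ratio of mean estimate to truth = (1.559 + φ(0.879)/0.1897)/1.559 = (1.559 + 0.2711/0.1897)/1.559 = 1.92.

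**Step 3: all looks.** Two million simulated trials per effect, stopping at the printed boundaries. Coverage is for estimate ± 1.96 SE.

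| Stop for efficacy at | Design effect: estimate/truth | Coverage | Half effect: estimate/truth | Coverage |
|---|---|---|---|---|
| Look 1 | 1.92 | 87% | 3.66 | 48% |
| Look 2 | 1.35 | 98.5% | 2.55 | 81% |
| Look 3 | 1.08 | 99.97% | 2.04 | 94% |
| Look 2 or 3 | 1.22 | 99.2% | 2.28 | 88% |

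In points, a look-2 or look-3 stop would report on average 1.22 × 104 ≈ 127 if the truth is 104, and 2.28 × 52 ≈ 119 if the truth is 52. The reported figure barely separates the two.

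**Step 4: coverage over all trials, stopped or not.** 94.7% at the design effect, 93.2% at half, 93.0% with no effect (91.7% at a quarter of the design effect).

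**Step 5: interval against test.** At the last look the two disagree when |z| lies between 1.96 and 2.397. This happens in 8.5% of trials at the design effect and 11.0% at half.

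**Step 6: sensitivity to timing.** With information 0.2, 0.4, 0.6, 1.0 and the 104-point effect tied to N=50, the look 1–3 ratios are 2.12, 1.49 and 1.19. A look-2 or look-3 stop averages 1.34 at the design effect, and 2.54 with 83% coverage at half. Step 5 becomes 9.0% and 11.6%.

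**The case against.** *The plan promises appropriate intervals, so a reader should not assume naive 95% ones.* This stands against one tempting inference, that the plan commits to uncorrected 95% intervals. It does not. The 95% figure is a sample-size input, and the text calls that level inadequate. What remains is that no method or level is named, and that the adjective describes the interval and not the effect size.

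*The twofold inflation belongs to a look already taken.* This also stands. SAP version 4 is dated 11/30/2020 and records outcomes added after the first interim analysis, with the trial continuing. Twofold is also the look-1 average under the design effect, not a ceiling: the ratio is higher when the true effect is smaller.

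*Under-coverage is not general.* Correct. Looks 2 and 3 over-cover at the design effect, and the overall shortfall is small.

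*SAP 6.4 already says which rule governs.* Correct for significance. A reader might infer that the plan leaves two rival verdicts, but the Pocock rule decides. An interval that excludes zero beside a non-significant test would still confuse, given how far the plan leans on intervals.

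*Stopping also needs a secondary outcome.* Assuming a correlation of 0.5–0.8 with the primary outcome, the same standardized effect and a threshold of z ≥ 1.96, this barely changes the inflation: early stops average 1.41–1.43 at the design effect, against 1.42 without the condition.

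**Conclusion.** The gap is real and of moderate size. The plan specifies a sequential correction for the test and none for the estimate or interval on which it relies. From look 2 onward, an efficacy stop overstates the effect by about a fifth if the design effect is true and by a factor of about 2.3 if half of it is true. Under-coverage of a 1.96-SE interval is modest overall and marked only after an early stop with a smaller true effect. The documents do not support a claim that estimates from this trial will in general be doubled, or that its intervals will broadly fail.

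The figures assume a normal approximation (with about 5 per arm at look 1 and 10 at look 2 the z boundaries are rough), stopping whenever the boundary is crossed, and one constant effect. Futility rules, crossover and the change to tPA50 plus drip after 20 patients were not modelled.

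**What to change.** 1. Reconcile row 4 of the SAP 3.2 table: either the last look is at 80% of the information or its boundary and alpha need recalculating for N=50.
2. State in SAP 3.3 and 6.4 that the primary-outcome interval at each look is a repeated confidence interval, with that look's Pocock boundary in place of 1.96. With the printed boundaries, overall coverage is 98.4% at the design effect, 98.1% at half and 95.7% with no effect.
3. If the trial stops early for efficacy, report a bias-adjusted estimate (for example Whitehead's) beside the mixed-model estimate, label the latter unadjusted, and use the adjusted figure for Phase III planning. At an average look-2 stop under the design effect, 1.35 times the truth becomes 1.14; at look 3, 1.08 becomes 0.89 (both with the last look at full information). A median-unbiased estimate from stage-wise ordering corrects less at these looks (1.27 and 0.97) and leaves a look-1 stop unchanged.
4. Note that any estimate pooled across the change of regimen at n=20 assumes a common effect.

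The cost is SAP wording and standard code. The interval is 22–24% wider than the 1.96-SE one (2.397/1.96 = 1.22; 2.438/1.96 = 1.24), or 16% wider at the last look if its boundary becomes 2.281. The headline effect is smaller after an early stop.

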### 3.3. Statistical interim analyses and stopping guidance:

#### ***Criteria for stopping the clinical trial early for efficacy or harm:***

Stopping the clinical trial early for efficacy or harm
Reaching adjusted p-value for the primary outcome and at least one of the secondary outcomes at all follow-up time points
DSMB deemed harm profile unacceptable

**Criteria for stopping for futility:** we will follow the guidelines established by Jitlal et al :

Stopping the clinical trial early for futility
•Low conditional power ( $\leq 15\%$ ), calculated using PASS 14 with bootstrapping simulations, based on the target minimum differences for all primary and secondary outcomes at all follow-up time points.
•Observed difference size in the primary or secondary outcomes favor the control group ( $< 5\%$ ) at all follow-up time points.
•The DSMB and trial team agree that enough patients and events have been observed so far to produce a reliable effect
•There are less than 2 centers interested in continuing enrollment
•There is no evidence of an effect in any pre-specified subgroups.
•The DSMB deemed the adverse events profile acceptable (if there are no safety concerns, we may wish to continue to ensure that a modest effect is not missed).

**3.4. Adaptive design:** The study interim analyses will be used to propose pre-planned modifications based on observed effects, recruitment, eligibility and other aspects of the study as determined below.

- Drop/add study arms: deploying study arms sequentially (vs in-parallel) allows sufficient sample sizes in each arm to assess outcomes and adverse events. Study arms that show significant improvement may ethically preclude the deployment of other arms. Similarly, study arms which show adverse events (as listed) attributable to the intervention (per trial team with DSMB /IRB determination) or minimal/no improvement may be eliminated. Study arms may be added if concurrent trials demonstrate significant evidence of benefit of a different route, dose, mode of administration of the study drugs.
- Inclusion criteria: although currently the trial entry criteria are based on age and PaO2/FiO2 we recognize the potential role of coagulation assays (for example D-Dimer, fibrinogen, fibrinolysis) in better defining the group most likely to benefit from the fibrinolytic intervention. Thus, such assays may be added as entry criteria if identified as predictors of good results during interim analyses or in other clinical trials. IN addition, if stratified analysis on initial PaO2/FiO2 shows benefit or harm in low and moderate PaO2/FiO2, the PaO2/FiO2 level for entry in the study may be modified to increase the probability of benefit.
- Sample size: the current sample size is defined by budget and feasibility constrains, and may prove insufficient if the effect detected is substantial but there is low power to detect it. A larger sample size may be recommended by the trial team and the DSMB, in which case we will pursue additional resources to increase enrollment.
- Cessation rules: based on interim analyses, coagulation and oxygenation variables may become important determinants of benefit/risk for the subjects as explained above, thus these variables may be proposed as further determinants for cessation rules.
- Enrollment/refusal rates

- Crossover: if one treatment arm shows a signal of benefit (as defined in our proposed outcomes), we are under the ethical mandate to offer it to patients who were enrolled in the other arms but did not show improvement. These patients “crossover” to the alternative arm. The analysis will be conducted as an intent-to-treat approach (patients are analyzed according to their initial assigned group) and subsequently in a separate as-treated analysis considering the combination of the two treatments.
- Comparison of prone/supine position: additional arms or change in entry criteria may have to be added if the prone position for ventilation is demonstrated to have a major benefit (e.g., criteria for entry may be modified to  $\text{PaO}_2/\text{FiO}_2 < 150$  in prone position)
- Doses/duration/administration mode of tPA and heparin: as more is learned during this trial as well as other clinical trials about the administration of tPA in relation to other ventilation techniques (prone position, PEEP, pulmonary vasodilators, etc.) and the risk/benefit associated with the doses, duration and mode of administration (e.g., bolus versus continuous drip), it may be beneficial for study subjects to modify the study arms.

**Proposed amendment 11/5/2020:** Per the adaptive plan above, changes in dose and mode of administration of tPA were pre-planned. Based on the first interim analysis and feedback from our DSMB, we propose to change the study arm in the second deployment of the intervention to the same dose and mode of administration of the first phase (i.e. 50mg bolus dose, with a second dose if necessary as prescribed above).

**Assuming NO stopping criteria (as described in the protocol) are met,** we will proceed as follows:

- 1) If at the end of the second intervention deployment (total of 20 patients randomized), the primary outcome ( $\text{PaO}_2/\text{FiO}_2$  ratio at 48 hours) improves by  $\geq 50\%$ , the study group will continue to receive the dose of the first phase (i.e. 50mg bolus dose, with a second dose if necessary as prescribed above) till the end of the study (total of 50 randomized patients). Interim analyses will be conducted as planned above, and submitted expeditiously to the DSMB, IRB and FDA for approval, yet enrollment will continue while these agencies deliberate and their feedback is received.
- 2) If at the end of the second intervention deployment (total of 20 patients randomized), the primary outcome improves ( $\text{PaO}_2/\text{FiO}_2$  ratio at 48 hours) by  $\geq 20\%$ , or the secondary outcomes  $\text{PaO}_2/\text{FiO}_2$  ratio at 24 hours improves  $\geq 20\%$ , or dead space decreases by 15%, or ICU- or ventilator-free days continue to exhibit a positive response (at least 2 days difference), we will modify the mode of administration of the second dose of tPA as follows: following the 50mg tPA bolus, we will initiate a drip of 2 mg/hr tPA over the ensuing 24 hours (total 48 mg infusion) accompanied by an infusion of 500 U heparin during the tPA drip. After this, heparin dose will be increased slowly to maintain a PTT between 60 and 80 sec, titrated per attending's discretion. Interim analyses will be conducted as planned above, and submitted expeditiously to the DSMB, IRB and FDA for approval, yet enrollment will continue while these agencies deliberate and their feedback is received.

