## Section 4: Statistical Principles

**4.1. Level of statistical significance:** see above description of p-value for interim analyses.

**4.2. Description and rationale for any adjustment for multiplicity of time points:** There will be no adjustment for multiple outcomes, as all were pre-planned. The investigator-statistician in charge ([name]) strongly agrees with the argument that adjustment for multiple comparisons in pre-planned hypotheses leads to more type II errors.

**4.3. Analysis populations:** all analyses, including safety analyses, will be conducted initially as **intention-to-treat** and then **as-treated**.

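### If crossover opens, the planned as-treated efficacy analysis regroups patients by failure to improve and by survival, so it does not estimate the effect of receiving tPA and cannot check the ITT result

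*SAP*

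**What the plan says.** SAP 3.4 (Adaptive design, Crossover item) makes crossover conditional: "if one treatment arm shows a signal of benefit (as defined in our proposed outcomes"), the trial team must "offer it to patients who were enrolled in the other arms but did not show improvement". These patients are analysed by ITT first and "subsequently in a separate as-treated analysis considering the combination of the two treatments". The Protocol's Crossover item under Adaptive design says the same.

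The as-treated analysis is not confined to crossover. SAP 6.4 states: "All analyses will be conducted initially as an intent-to-treat (patients are analyzed in the group they were randomized to), followed by an as-treated analysis". The Protocol's Statistical analysis section repeats this. SAP 4.3 extends the order to safety: "all analyses, including safety analyses, will be conducted initially as" intention-to-treat, and then as-treated.

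SAP 6.4 describes the adjustment. The mixed model is to "adjust for potential confounders detected in the comparison of the groups at baseline using inverse probability weighting" by a propensity score, and mortality uses an "inverse probability weighted Cox proportional hazards model and robust sandwich variance estimate with clustering for hospitals".

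Neither document gives an as-treated grouping rule, a crossover time, a time-dependent exposure, a landmark, or a limit on how the as-treated result may be interpreted.

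**The concern.** An as-treated comparison is fair only if the reasons for changing group are unrelated to outcome. Here the stated reason is the outcome itself: a control leaves control because of not improving, and can leave only by living long enough to be treated. The controls who remain are therefore improvers, non-improvers who did not take up the offer, and patients who died before they could cross. A baseline propensity score contains none of that information.

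At stake is how the second analysis is read. SAP 3.2 rejects a rigid significance cutoff and asks the investigators and the DSMB to interpret effect sizes in order to inform medical decisions and the next Phase III trial. An as-treated estimate placed beside ITT without a warning would be taken as confirming or weakening it, and it can do neither.

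Safety has the opposite problem. With ITT leading, a bleed after crossover alteplase counts against control in the lead table, which dilutes the bleeding contrast for a fibrinolytic.

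**Working it through.** The plan gives no figure for the as-treated analysis, so there is none to reproduce. The check asks what an inert drug would show.

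**Inputs.** From the documents: SD 100 for P/F (SAP 3.2, where it is called overestimated, so SD 50 is also shown); 25 versus 25 patients (SAP 3.2); 28-day follow-up (Protocol, Follow-up); mortality of 22-64% (Protocol, Abstract), with 40% used here. Assumed, because the documents give no values: mean P/F change of +30 in both arms at 24 h and 48 h, correlation 0.6 between the two changes, non-improvement defined as a gain under 20 points at 24 h, and exponential survival.

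**1. P/F at 48 h, crossovers taken out of control.** Let a = (20 - 30)/SD and p = Φ(a), the share of non-improvers.
- Mean shift of improvers: 0.6 × SD × φ(a)/(1 - p). Mean shift of non-improvers: -0.6 × SD × φ(a)/p.
- SD 100: a = -0.1, p = 0.460, φ = 0.397. Improvers shift by 60 × 0.397/0.540 = +44.1; non-improvers by -60 × 0.397/0.460 = -51.8.
- All non-improvers cross: remaining controls average 30 + 44 = +74 against +30 for tPA. Bias **-44**.
- Half cross: (0.540 × 44.1 - 0.230 × 51.8)/0.770 = +15.5. Bias **-15**.
- SD 50: a = -0.2, p = 0.421, φ = 0.391. Improvers shift by 30 × 0.391/0.579 = +20.3; non-improvers by -30 × 0.391/0.421 = -27.9. All cross: **-20**. Half cross: (0.579 × 20.3 - 0.210 × 27.9)/0.790 = 7.4, bias **-7**.
- If crossovers are pooled with tPA (SD 100, all cross), the tPA group falls by 0.460 × 51.8/1.460 = 16.3, and the bias is -44.1 - 16.3 = -60. With half crossing it is -25.

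Grouped as randomised, simulated inert-drug trials (25 versus 25, SD 100) gave a mean difference within 0.4 of zero and about 2% rejection at the final boundary of 2.397.

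**2. Mortality at 28 days, any tPA versus control only.** Assume half of patients are non-improvers, with death hazard k times that of improvers, and that every non-improving control alive on the crossover day crosses. Per randomised control, let c be the share crossing and d the share crossing and later dying. Risk is (0.40 + d)/(1 + c) for any tPA and (0.40 - d)/(1 - c) for control only.
- Day 4, k = 1: c = 0.465, d = 0.165. Risks 0.565/1.465 = 38.6% and 0.235/0.535 = 43.9%; OR 0.80.
- Day 1, k = 1.5: c = 0.489, d = 0.220. Risks 0.620/1.489 = 41.6% and 0.180/0.511 = 35.2%; OR 1.31.

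| Crossover day | k = 1 | k = 1.5 | k = 2 |
|---|---|---|---|
| 1 | 0.94 | 1.31 | 1.66 |
| 4 | 0.80 | 1.06 | 1.28 |

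Survival to crossover pulls the OR below 1, and selection of non-improvers pushes it above 1. The net sign depends on two quantities that the documents do not give.

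**3. Does time-dependent exposure repair mortality?** In part. For an inert drug the rate ratio returns to 1.00 at k = 1, but at k = 1.5 it is still 1.08 to 1.28 across crossover days 2 to 14 and mortality of 22-64%. The survival artefact is removed; selection on non-improvement is not.

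**The case against.** The best defence is that this is a secondary analysis. ITT comes first in every passage, no stopping or adaptation rule uses the as-treated result, and crossover is conditional and absent from the deployment sequence in SAP 3.1. All of that stands and limits the importance of the point.

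Timing is the second defence. If non-improvement is judged on the 48-hour primary outcome, no crossover dose precedes that measurement, and a grouping that respects time leaves the 48-hour P/F comparison as randomised. This also stands: the P/F bias needs crossovers to be taken out of control for that outcome, and the SAP does not say whether they would be. The wording about combining the two treatments may also mean a separate category rather than pooling. The -44 and -15 above already take the separate-category reading, and the sign is unchanged.

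Two stronger readings are tempting. One is that the bias reverses between outcomes, so that an inert drug looks harmful on P/F and protective on mortality. The protective figure needs crossover unrelated to prognosis, or late crossover, whereas the plan selects patients who have not improved; with early crossover and a modestly worse prognosis, both outcomes point to harm. The other is that patients randomised to tPA who die undosed will be moved into control. No passage says so, and any count of such deaths would be invented.

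On safety, both tables are planned and SAP 7 ties relatedness to a 3-hour window after drug. That limits the harm but does not change which table leads.

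**Conclusion.** The concern holds as a conditional one about a secondary analysis. If crossover opens, the as-treated efficacy comparison is not protected by randomisation, and the planned baseline weighting does not restore that protection.

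For P/F the direction is against tPA whenever crossovers are taken out of control for that outcome: about -44 or -15 points at SD 100 and -20 or -7 at SD 50, for full and half crossover. The sizes rest on the assumed correlation, cutoff, timing and uptake; the direction follows from removing non-improvers from control. For mortality the bias can go either way (OR 0.80 to 1.66 for an inert drug in the cases shown), so a claim of opposite bias on the two outcomes is not supported. The unpredictable sign is itself reason enough not to use the analysis as a check on ITT.

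The primary ITT result is not directly threatened. For safety, leading with ITT places bleeds after crossover alteplase in the control column. The change should be made, because it is cheap and the estimate would otherwise be read without a warning.

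**What to change.** Edit SAP 3.4, 4.3 and 6.4, and the matching Protocol text (the Crossover item under Adaptive design, and Statistical analysis), so that the documents stay in agreement.

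1. Make ITT the only basis for efficacy conclusions.
2. If controls cross over, replace the as-treated efficacy comparison with a randomisation-based estimate: the ITT difference divided by the between-arm difference in the proportion who received tPA by the outcome time. Crossover from tPA50 to tPA50 plus drip is invisible to that denominator and needs its own contrast, or ITT only.
3. Label any as-treated, received-dose or time-dependent-exposure efficacy analysis exploratory. State that time-dependent exposure removes the survival artefact but not selection on non-improvement.
4. Lead safety with the as-treated analysis: exposure starts at the first alteplase dose, earlier events count as unexposed, and ITT safety is reported alongside.

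The cost is SAP and Protocol wording and modest programming. The randomisation-based estimate is less precise: with the whole tPA arm dosed and 46% or 23% of controls crossing (the SD 100 cases above), its standard error is roughly the ITT one times 1/0.54 = 1.85 or 1/0.77 = 1.30, and it treats a late dose as equal to one given at randomisation. After crossover the exposed safety group will include non-improvers, which the report should state.
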